One strategy for enhancing engagement and completion of a brief intervention targeting perceived burdensomeness is to embed it within existing psychosocial treatments for youth psychopathology (e.g., cognitive-behavioral therapy [CBT] for youth anxiety disorders). Consistent with a modular CBT approach⁸, this strategy would enable clinicians to select and employ a brief intervention module when youth clients demonstrate thoughts of being a burden on others, with minimal disruption to the ongoing intervention protocol.

The purposes of this project are to (1) develop a novel, brief psychosocial intervention module (the GIVE module) targeting perceived burdensomeness towards others that can be embedded within existing CBT protocols for youth internalizing problems, and then (2) collect data relevant to the timing of reductions in perceived burdensomeness. The following aims will be pursued with N=30 clinic referred youths ages 10 to 17 who are receiving outpatient CBT for anxiety or depression.

Aim 1: Develop a manualized module targeting perceived burdensomeness to be used as an adjunct to existing psychosocial treatments. The GIVE module will consist of one core intervention session involving the youth and a parent (approx. 50 minutes) and one follow-up discussion of homework completion (approx. 10 minutes).

Aim 2: In an open trial, examine adherence and satisfaction with the GIVE module. Adherence, operationalized as provider fidelity and integrity, will be assessed by coding recorded session content. Youth and parent satisfaction will be assessed using the Client Satisfaction Questionnaire.

Aim 3: In an open trial, demonstrate reductions in youth levels of perceived burdensomeness. Perceived burdensomeness will be assessed at pretreatment (PRE), midtreatment (MID; i.e., CBT session 6), every treatment session, and posttreatment (POST). We expect that perceived burdensomeness will be significantly lower at POST relative to MID (i.e., CBT session 6, immediately before beginning the GIVE module).

APPROACH

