General overview. Following parental consent and youth assent, parents and youths will be administered interviews and questionnaires as part of PRE assessment to determine eligibility for this study (see Inclusion/Exclusion criteria). Eligible youths will be allocated to a 12-session CBT protocol with an additional module targeting perceived burdensomeness to be administered during CBT session 6. Youth participants' levels of perceived burdensomeness will be assessed weekly at the beginning of each session of the CBT protocol and again at a POST assessment one week after the final CBT session.

Participants. N=30 youths ages 10 to 17 years will be recruited upon entry into clinical services for anxiety and/or depression.

Inclusion criteria. To be included in this study, youth must: 1) be between ages 10 to 17 years old; 2) meet for a primary DSM-V diagnosis of an anxiety disorder, persistent depressive disorder, or major depressive disorder; 3) score ≥ 4 on the youth self-report Interpersonal Needs Questionnaire- Perceived Burdenomeness

Scale at PRE and again at CBT session 5; and 4) if youth have ADHD, tics, or impulse control problems, those disorders must receive an impairment rating no greater than 4 ('Moderate') on the 0–8 point scale on the Anxiety Disorders Interview Schedule Child/Parent versions (ADIS-C/P).

Exclusion criteria. Youth will be excluded from this study if they: 1) meet diagnostic criteria for Psychotic Disorders, Autism Spectrum Disorder or Intellectual Disability, 2) show high risk of imminent self-injurious behaviors, 3) are involved currently in another psychosocial treatment; 4) are not living with a primary caregiver who is legally able to give consent for the youth's participation, or 5) are a victim of previously undisclosed abuse requiring investigation or ongoing supervision by the Department of Social Services.

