GIVE module. The GIVE module will include three components: (1) in-session cognitive restructuring, introduced by a brief rationale and psychoeducation; (2) a home assignment to be completed by youth; (3) a parent component providing psychoeducation on burdensomeness that sets up a brief parent-child relationship task. Table 1 provides an outline of the core session of the module, and the follow-up session. The module will be briefly introduced to youth with a rationale outlining the importance of addressing specific negative beliefs that may appear as secondary to the presenting problem but which are nonetheless critical to address, particularly perceived burdensomeness; this brief rationale will be followed by psychoeducation on what fosters this negative belief and outcomes related to this belief (overall introduction is approximately 5 minutes). The first major component of the GIVE module (during the subsequent 15 minutes of session 6), in-session cognitive restructuring with the youth only, consists of identifying negative thoughts (i.e., burdensomeness) using real-life examples and then collaboratively evaluating cognitions of burdensomeness using techniques such as reality testing and cost-benefit analysis¹⁸, with the aim of developing and shaping more adaptive cognitions. Cognitive restructuring will be conducted in a developmentally appropriate manner based on empirically-supported CBT protocols for youth. Consistent with the priority of minimal disruption to ongoing treatment, session 6 is an ideal session to introduce the module because it will leverage existing CBT skills covered earlier in treatment (i.e., cognitive restructuring).

Table 1. Module Outline

Core Session (session 6 of CBT protocol)	
 5 minutes: Rationale for module and psychoeducation on burdensomeness 15 minutes: Cognitive restructuring of burdensomeness 15 minutes: Planning home behavioral assignment 5 minutes: Psychoeducation on parental acceptance 10 minutes: Parental acceptance activity (positive qualities and ways to show acceptance lists)
Follow-up Session (session 7 of CBT protocol)	
 5 minutes: Discussion of home behavioral assignment 5 minutes: Wrap-up Resume ongoing CBT

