Aim 3: Demonstrate reductions in youth levels of perceived burdensomeness. Reductions in levels of perceived burdensomeness will be examined using two approaches. In the first, a paired samples t-test will be conducted to examine changes in mean scores from MID (i.e., session 6 INQ10-PB score) to POST. A priori power analysis for the paired-samples t-test indicated that N=27 would provide sufficient power to detect a medium effect size, thus the current study would have adequate power. In the second, segmented regression analysis will be conducted by the applicant to preliminarily gain insight into the timing and maintenance of changes in levels of perceived burdensomeness. The segmented regression method is a powerful analysis for a quasi-experimental, interrupted time-series designs²⁸⁻²⁹, recommended for small samples²⁸. In segmented regression analysis, session to session assessments of perceived burdensomeness will be used to examine the slopes in perceived burdensomeness before and after intervention in CBT session 6. The intervention effect is examined by statistically comparing the PRE and POST intervention slopes. In an interrupted time-series design, it is recommended that observations be equally balanced between pre intervention and post intervention (e.g., 6 observations before and after), and for the PRE assessment variability to be reduced (e.g., only selecting youth with higher PB for the study) to maximize power²⁸. For this reason, there are six assessment points (administrations of INQ10-PB) planned prior to and after the administration of the module for a total of 12 observations, and only youth with elevated PB will be recruited (i.e., variability reduction). The segmented regression analysis is intended to be preliminary to gain insight into the timing of changes, and as such, may be underpowered by design.

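### Does a session-5 re-screen undermine the step from 27 required pairs to adequate power with 30 youths?

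*Combined protocol and SAP*

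**What the plan says.** The Statistical Analysis Plan, Aim 3, tests the change in burdensomeness from MID (session 6) to POST with a paired t-test. It states that the power analysis "indicated that N=27 would provide sufficient power to detect a medium effect size, thus the current study would have adequate power". It gives no alpha, sidedness, numerical effect size, target power or allowance for loss.

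The aims say: "The following aims will be pursued with N=30 clinic referred youths ages 10 to 17 who are receiving outpatient CBT". Under Participants: "N=30 youths ages 10 to 17 years will be recruited upon entry into clinical services". Inclusion criterion 3, which follows directly, requires a score of at least 4 on the burdensomeness "Scale at PRE and again at CBT session 5".

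The General overview describes the PRE interviews and questionnaires "as part of PRE assessment to determine eligibility for this study", with a pointer to the full criteria, and then says: "Eligible youths will be allocated to a 12-session CBT protocol with an additional module targeting perceived burdensomeness". The last measurement comes "again at a POST assessment one week after the final CBT session".

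The opening paragraph of the Statistical Analysis Plan provides for full information maximum likelihood for missing values where it applies.

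**The concern.** The 27 in the power statement must mean complete MID-to-POST pairs, whereas the 30 under Participants reads like a count at entry. Between the two lie the session-5 score, attendance at session 6, the remaining sessions and the POST visit.

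A fall below 4 by session 5 is credible, because the GIVE module section says of session 6 that "it will leverage existing CBT skills covered earlier in treatment (i.e., cognitive restructuring"). Youths will therefore already have had some active treatment of negative thinking by then.

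The General overview also reads as if eligibility were settled at PRE. Criterion 3 cannot be complete until the start of session 5, after allocation and four completed sessions.

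Two things would be at stake. One is the plan's only sample-size justification for the test on its primary outcome. The other is the analysis set: all youths allocated at PRE, or only those still at 4 or above at session 5. That choice affects the MID mean and how a null result is read.

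**Working it through.** **Inputs.** Required number 27 and a medium effect (Statistical Analysis Plan, Aim 3); planned number 30 (aims and Participants). Assumed, because not stated: standardized mean change dz = 0.5, one-sided alpha 5% (the Aim 3 hypothesis is directional) and target power 80%. Loss rates are also assumptions; the documents give none for this design.

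**Reproducing 27.** Power of a one-sided paired t-test with n pairs is P(T > t₀.₉₅,ₙ₋₁), where T is noncentral t with n − 1 degrees of freedom and noncentrality dz·√n.

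- n = 27: noncentrality 0.5 × √27 = 2.598, critical value 1.706, power 81.2%.
- n = 26: noncentrality 0.5 × √26 = 2.550, critical value 1.708, power 79.8%.

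So 27 is the smallest number that reaches 80%, and the plan's figure reproduces. A two-sided 5% test at the same dz would need 34, so that is not the setting behind the 27.

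**Margin.** 30 − 27 = 3, and 3/30 = 10%. As two steps, 5% re-screen failure and 5% later loss leave 30 × 0.95 × 0.95 = 27.1 expected pairs. With 10% at each step, 30 × 0.90 × 0.90 = 24.3.

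**Power by number of pairs (one-sided 5%, dz = 0.5).**

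| Pairs | Power |
|---|---|
| 30 | 84.8% |
| 27 | 81.2% |
| 26 | 79.8% |
| 24 | 76.8% |
| 21 | 71.5% |

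**Allowing for random loss from 30 at entry.** Let the number of pairs K be binomial(30, 1 − loss). Average power is the sum over k of P(K = k) × power(k).

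| Assumed combined loss | Expected pairs | P(K ≥ 27) | Average power |
|---|---|---|---|
| 5% | 28.5 | 93.9% | 83.0% |
| 10% | 27.0 | 64.7% | 81.1% |
| 15% | 25.5 | 32.2% | 78.9% |
| 20% | 24.0 | 12.3% | 76.5% |

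The third column looks alarming, but it is the chance of reaching a particular count, not the chance of detecting the effect. The fourth column answers the power question. At 20% loss the shortfall against 80% is 80 − 76.5 = 3.5 percentage points.

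**Which 30?** If the 30 are counted at entry, the 3 spare youths cover re-screen failures and all later loss, as tabulated. If the 30 are youths who meet every inclusion criterion, re-screen failures are not among them, and the 3 cover only loss from session 5 to POST. The text allows the second reading: the criteria follow the Participants statement directly, criterion 3 contains the session-5 score, and the General overview refers the reader to those criteria.

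**The case for a change.** The strongest case for a change is that the wording under Participants counts youths on entry, and the word thus in the power statement then needs combined loss of no more than 3 in 30. The plan states no loss rate, inflation or replacement rule. Only the segmented regression is described as preliminary and possibly underpowered; for the t-test, adequacy is asserted. Nor does full information maximum likelihood rescue the margin. A paired t-test uses complete pairs, and a youth who is not included at session 5 is not a missing value. On the second reading, the number to be recruited at entry is not given.

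Much of this is accurate. The denominator is undefined, the loss assumption is unstated, and the General overview compresses a two-stage eligibility rule into one sentence. The point about likelihood methods holds for re-screen failures and for a literal complete-pair test. It is weaker for a youth missing only POST, whose weekly scores could inform a likelihood-based estimate of the mean change.

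What does not stand is the inference that adequacy fails. That needs a loss rate above 10%, and the documents supply none for this design. The only figure, about 50% non-completion in the sponsor's earlier study, concerns online modules. It does not measure missed POST assessments in clinic-delivered CBT.

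**Conclusion.** No change to the plan follows. The 27 is correct on the setting that reproduces it, and 30 already carries a 10% allowance. Average power is about 81% at 10% loss and about 77% at 20%. For an open trial of 30 youths, a possible shortfall of about 3.5 points under an assumed rate is not a demonstrated power failure.

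The remaining matter is missing detail of a kind that analysts fill sensibly. Criterion 3 identifies who is included, the paired test then runs from session 6 to POST on those youths, and the counts at PRE, session 5, MID and POST show what was lost. Run as written, that test is sound. Writing these points down would make the plan clearer, but would alter neither the test nor its validity. Enrolling more youths or restating power would rest on a loss rate that the documents do not contain.

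This conclusion assumes a one-sided 5% test, dz = 0.5 and losses that are independent between youths. The unstated alpha and sidedness are a separate matter and do not affect the 3-youth margin.

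### The segmented regression's only stated effect is a slope difference, which is zero or near zero for an immediate, maintained drop after session 6; a level change should be reported beside it.

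*Combined protocol and SAP*

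**What the plan says.** The Statistical Analysis Plan gives Aim 3 two analyses. In the first, "a paired samples t-test will be conducted to examine changes in mean scores from MID" to POST. The second is a segmented regression intended to "preliminarily gain insight into the timing and maintenance of changes in levels of perceived burdensomeness".

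For the second analysis, the session scores "will be used to examine the slopes in perceived burdensomeness before and after intervention in CBT session 6", and then: "The intervention effect is examined by statistically comparing the PRE and POST intervention slopes". Both sentences name slopes only. The plan gives no model equation, no knot, and no step, level or intercept-shift term. It does not exclude such a term either.

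On layout, the plan says that "there are six assessment points (administrations of INQ10-PB) planned prior to and after the administration of the module for a total of 12 observations". The General overview places each weekly score at the beginning of its session, and Aim 3 places MID at session 6, "immediately before beginning the GIVE module". Session 6 is therefore the last score before the module and session 7 the first after it. POST follows one week after session 12.

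The plan limits its own claim: "The segmented regression analysis is intended to be preliminary to gain insight into the timing of changes". It adds that this analysis may be underpowered.

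**The concern.** The stated purpose concerns levels, but the only contrast called the effect concerns slopes. These differ when the response is abrupt. Table 1 puts the core of the module in session 6, with ten minutes of follow-up in session 7. If burdensomeness falls by session 7 and stays down, the lines before and after the module are parallel. A slope comparison then reports no effect however large the fall.

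At stake is the information this analysis was added to supply: when the change occurred and whether it lasted. The t-test uses two time points, so it cannot supply this.

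**Working it through.** **Inputs.** From the documents: 12 scores (sessions 1-6 before the module, 7-12 after) and N=30. The documents give no variances or correlations for INQ10-PB. Assumed: between-youth SD 1, random-slope SD 0.05, within-youth SD 0.5, 0.7 or 1.0, lag-1 autocorrelation (AR(1)) 0.3 unless stated, two-sided 5% tests on per-youth coefficients.

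**1. The plan's own figure.** The plan's only sample-size figure is N=27 for the paired t-test at a medium effect (taken as d=0.5). Exact noncentral-t power at N=27 is 81.2% one-sided and 70.6% two-sided at 5%, so 27 matches a one-sided 5% test at 80% power. The plan states neither sidedness nor power. It gives no figure for the segmented regression, and nothing below depends on N=27.

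**2. Separate lines.** Let the score be a + bt for t = 1 to 6 and a + bt - D for t = 7 to 12, a drop of D that holds. The fitted post-module slope is

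Σ(t - 9.5)y / Σ(t - 9.5)² = b - D × Σ(t - 9.5) / 17.5 = b - D × 0 / 17.5 = b.

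The pre-module slope is also b, so the slope change is 0 for any D and any CBT trend b. The level change is -D. Both results hold with or without session 5, and with or without POST.

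**3. Joined lines, no level term.** Fit a + bt + c × max(t - k, 0) to a unit drop at session 7. The slope change c, per session, is:

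| Knot k | All 12 scores | Without session 5 |
|---|---|---|
| 6 | -0.041 | -0.007 |
| 6.5 | 0 | +0.032 |
| 7 | +0.041 | +0.067 |

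This fit also creates a false pre-module decline of about 0.10 to 0.15 of the drop per session, so part of the drop is credited to the CBT sessions before the module.

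**4. A drop that does not hold.** If a unit drop at session 7 fades linearly to nothing at session 12, the separate-lines slope change is 1/5 = +0.2 per session. Read alone, that looks like worsening, with no sign of the benefit that preceded it.

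**5. Rejection rates for a maintained drop of 0.5 SD** (N=30, 5,000 trials, within-youth SD 0.5 / 0.7 / 1.0):

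| Test | Rejection |
|---|---|
| Planned slope change | 5 / 5 / 5% |
| Level change, session 5 omitted | 99 / 83 / 56% |
| MID to POST t-test | 92 / 70 / 44% |

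A second simulation used all 12 scores (4,000 trials, within-youth SD 1, AR(1) 0 or 0.4). For a 1-SD drop it gave 5.0-5.2% for slope and 98.7-99.5% for level. For a 0.5-SD drop it gave 5.0-5.1% and 56-62%.

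**6. What the level term cannot separate.** Suppose the effect is purely gradual, a change of -g per session starting after session 6. At session 7 the score is already g below the projected trend, so a level change evaluated at session 7 is -g. In simulation, such effects made that term significant in about 10-30% of trials.

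**7. Selection on session 5.** The Inclusion criteria require a score of at least 4 at PRE and again at session 5. With no true effect and an assumed cut-off between -1 and +0.5 SD (4,000 trials per setting, AR(1) 0 or 0.3), false positives were:

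| Fit | Slope | Level |
|---|---|---|
| With session 5 | 5-12% | 5-29% |
| Without session 5 | 5-6% | 5-9% |

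At AR(1) 0.5-0.7 with higher cut-offs (0 and +0.5 SD), and without session 5, the level term reached 7-14% and the slope 5-9%.

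**The case against.** **A slope contrast is a legitimate effect measure.** The home assignment and the wrap-up on using the tools later fit a gradual response, and nothing in the documents predicts a step. This stands as a reason to keep the slope test. It is not a reason to report only that test when the stated purpose is changes in level.

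**The plan is silent, not wrong.** No equation is given, and two separately fitted lines would yield a level shift anyway. A reader might infer that the plan rules out a level term; the documents do not support that. But even if a level shift is estimated, the plan does not count it as the effect, and choosing it after seeing the data would be post hoc.

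**The trial would still detect the drop.** This stands. A reader might infer that Aim 3 is blind to an immediate drop, but the t-test would register it. The gap is confined to timing and maintenance.

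**The analysis is declared preliminary and possibly underpowered.** This lowers the consequence. It does not cover the problem: more youths or sessions would improve power, but would not move a contrast whose expected value is zero.

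**The level term is more exposed to selection than the slope.** This stands, on the figures in step 7, and is why the level change belongs in the report as a preliminary estimate and not as a second test. It does not justify making a fit without session 5 the main analysis. The plan deliberately balances six scores on each side, and the size of the bias rests on assumed cut-offs.

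**Conclusion.** The point holds for the second Aim 3 analysis only. For an immediate, maintained drop the stated contrast is exactly zero with separate lines. With joined lines it is within ±0.041 of the drop per session on all 12 scores. These results are algebra and need no variance assumption; the power and false-positive figures rest on the assumed values given with the working. As written, the segmented regression would not show the timing or maintenance of such a change.

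The change is worth making, but the consequence is modest because the t-test remains and the analysis is preliminary. A reader might also infer that a significant level change would prove an immediate effect of GIVE. It would not: it can contain the first week of a gradual effect, and selection on session 5 can imitate it.

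**What to change.** In the Statistical Analysis Plan, Aim 3, replace the sentence that defines the intervention effect with:

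*The model for the session 1-12 scores has a pre-module slope, a level change between sessions 6 and 7 (evaluated at session 7 against the projected pre-module trend) and a slope change after the module, with within-youth correlation. The slope change is tested as planned; the level change is reported beside it as an estimate with a 95% confidence interval, as preliminary and outside the Holm family. Because eligibility uses the session 5 score, which can produce an apparent drop, the model is also fitted without session 5 and both sets of estimates are reported.*

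**Cost.** One more parameter, one sensitivity fit and SAP wording; no new data. Keeping the level change outside the Holm family protects the t-test. If an experiment-wise family grew from two tests to three, the strictest threshold would fall from 0.05/2 = 0.025 to 0.05/3 = 0.0167. Worst-case two-sided t-test power at d=0.5 and N=30 would then fall from 65% to 58%.

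**Remaining limits.** Under the assumed settings, selection could produce a false level change in up to about 29% of trials with session 5. Without it the figure is up to about 9% at AR(1) 0.3 and 14% at 0.7. The level change must be read together with the slope change, because it absorbs the first week of any gradual effect.

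### The slope difference tested at a break fixed at session 6 does not by itself show when burdensomeness starts to fall, although timing is a stated purpose

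*Combined protocol and SAP*

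**What the plan says.** The paragraph on the purposes of the project gives the second purpose as to "collect data relevant to the timing of reductions in perceived burdensomeness". In the Statistical Analysis Plan, Aim 3, the segmented regression is there to "preliminarily gain insight into the timing and maintenance of changes in levels of perceived burdensomeness".

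The break is set in advance: the session scores are used to "examine the slopes in perceived burdensomeness before and after intervention in CBT session 6". The inference is one contrast: "The intervention effect is examined by statistically comparing the PRE and POST intervention slopes". On the data, the same paragraph says "there are six assessment points (administrations of INQ10-PB) planned prior to and after the administration of the module for a total of 12 observations". The General overview says that burdensomeness "will be assessed weekly at the beginning of each session of the CBT protocol", so the session 6 score is taken before the module is delivered.

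The plan does not describe an estimated break, alternative breaks, a lag, a level-change term or session-by-session contrasts. It also does not say whether the two lines are fitted separately or joined. The other Aim 3 analysis uses two time points and carries no timing information: "a paired samples t-test will be conducted to examine changes in mean scores from MID (i.e., session 6 INQ10-PB score) to POST".

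The GIVE module section explains the choice of session 6: "it will leverage existing CBT skills covered earlier in treatment (i.e., cognitive restructuring". Cognitive restructuring is also the first major component of the module.

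**The concern.** The weekly scores are meant to show when burdensomeness changes, but the tested quantity takes the date of change as given and asks only whether the slope differs on either side of it. An earlier start is plausible here, because youths have already met cognitive restructuring in the CBT sessions before the module. The trial is open, with no control arm, so the slope contrast is the main means of separating GIVE from the CBT that surrounds it.

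If a decline begins before session 6 and continues, the pre-module line averages flat and falling weeks and comes out too shallow. Part of the earlier decline is then counted as an intervention effect. If an early gain levels off, the reverse happens. In either case the report could date the change wrongly while the weekly data that bear on the question go unused.

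**Working it through.** **Inputs.** Twelve scores per youth, six before and six after the module (SAP, Aim 3). Taking these as sessions 1-12 scored at the start of each session (General overview), sessions 1-6 precede the module and sessions 7-12 follow it. This reproduces the plan's six-and-six split. The plan gives no other figure for this analysis; its N=27 belongs to the paired t-test.

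**Formula.** For six equally spaced scores y, the least-squares slope is the sum of d × y divided by 17.5, where d = -2.5, -1.5, -0.5, 0.5, 1.5, 2.5 and 17.5 is the sum of d squared. The tested contrast is the post-module slope minus the pre-module slope. Scores are written as change from a flat start, without noise.

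**Sustained fall of b per session, separate lines.**

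- First seen at session 6. Pre scores 0, 0, 0, 0, 0, -b: slope 2.5 × (-b) / 17.5 = -0.143b. Post scores -2b to -7b: slope -1.000b. Contrast **-0.857b**.
- First seen at session 9. Pre slope 0. Post scores 0, 0, -b, -2b, -3b, -4b: (0.5 - 1.0 - 4.5 - 10.0)b / 17.5 = -15b / 17.5 = -0.857b. Contrast **-0.857b**.

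The same calculation for other onsets:

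| Fall first seen at session | Pre slope | Post slope | Contrast |
|---|---|---|---|
| 4 | -0.629b | -1.000b | -0.371b |
| 5 | -0.371b | -1.000b | -0.629b |
| 6 | -0.143b | -1.000b | -0.857b |
| 7 | 0 | -1.000b | -1.000b |
| 8 | 0 | -1.000b | -1.000b |
| 9 | 0 | -0.857b | -0.857b |
| 10 | 0 | -0.629b | -0.629b |

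**Joined line bending at session 6.** The contrast is -0.877b (first seen at 6) and -0.802b (first seen at 9): close, but not equal.

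**Falls that stop, separate lines.**

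- One-step drop first seen at session 7: both segments are flat, so the contrast is 0.
- One-step drop of 3 points first seen at session 4: pre slope -3 × (0.5 + 1.5 + 2.5) / 17.5 = -0.771, post slope 0, contrast +0.771.
- Fall of 1 point per session for three sessions, first seen at session 5: pre slope (-1.5 - 5.0) / 17.5 = -0.371, post slope 0, contrast +0.371.

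**What the other fitted terms show.** For the pair at sessions 6 and 9, the level change read at session 7 is -1.333b against +0.476b, and the pre slope is -0.143b against 0. These terms do carry information on onset.

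**How visible that is at N=30.** The documents give no SDs. A simulation assumed SDs of 3 (intercept), 0.3 per session (slope) and 3 (residual), with a sustained fall of 0.5 points per session. With separate lines, the slope contrast was significant in 36% of runs when the fall was first seen at session 5 and in 38% when first seen at session 10. For the session 5 case, a pre-module slope was detected in 25% of runs (separate lines) to 37% (joined line).

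**Freeing the break.** Under the same assumptions, the best-fitting single break had a median at session 4, 6 or 9 when that was the last flat session before a sustained fall. For a three-session fall it failed: the median break was 8 when the last flat session was 4, and 5 when it was 6.

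**The case against.** A break fixed at the known intervention date is what the interrupted time-series design named in the SAP calls for; a searched break is an extra, exploratory step. The purpose is worded as collecting data relevant to timing, and the plan calls this analysis preliminary and possibly underpowered. Youths must also score at least 4 again at CBT session 5, which keeps out some who improved early. All of this stands, and the session-6 model should stay. But the preliminary label concedes low power, not that the contrast leaves onset undated, and the session 5 threshold does not exclude a decline that stays at or above 4.

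A reader might infer that the analysis gives the same answer for early and late onset. The documents do not support that. The plan says it will examine the slopes before and after, and those slopes differ. Exact equality holds only for the contrast, for sustained linear falls and for separately fitted lines, which the plan does not specify.

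A reader might also infer that ordinary CBT improvement will always make an inert module look effective. That needs the early decline to continue through the later sessions; if it levels off, the contrast turns positive and the module is understated.

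**Conclusion.** The point holds in a limited form. Timing is a stated purpose, one analysis is assigned to it, and the contrast that analysis tests does not identify when the fall starts. For a sustained fall first seen at session 6, before the module has been delivered, the contrast is already 86% of its value for a fall first seen at session 7, and it is the same as for a fall first seen at session 9. An immediate one-step drop after the module gives zero with separate lines.

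The slope figures are exact arithmetic for the stated paths on sessions 1-12. The detection rates rest on assumed SDs and an assumed fall of 0.5 points per session, and would change with other values. The pre slope, post slope and level change do help to separate early from late onset. The plan gives no rule for reading them beside the contrast, and at N=30 the pre-slope signal may be weak.

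**What to change.** Keep the session-6 model, state whether the lines are separate or joined, and add to the Aim 3 text:

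- (a) session-by-session mean change in INQ10-PB with confidence intervals, from a repeated-measures model with session as a category;
- (b) the pre slope, post slope and level change at session 6, reported together with the slope difference;
- (c) as a descriptive sensitivity analysis, the same model refitted with the break at each of sessions 3 to 9, marking the session at which cognitive restructuring is introduced.

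Item (a) is needed as well as (c), because one movable break misplaces a fall that levels off. Describe the slope difference as change during CBT plus GIVE, to be read beside the session-by-session profile.

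Do not make the module claim depend on which break fits best. Under the assumed SDs and a joined line, the session-6 break beat the earlier ones in only about 58 to 61% of runs when the fall truly began straight after session 6, and in about 71% when it began two sessions later. Such a rule would often reject a real effect and would not screen out a delayed one.

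The cost is SAP wording and a few more model fits, with no new data. Intervals will be wide at N=30, and the module claim may be weaker.
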